9.7.4 Immunogenicity

Immunogenicity assays will be performed on plasma. The assays will include detection of anti-capsid, and anti-FVIII total antibody, and determination of neutralizing antibodies against FVIII. Any increase in total antibody level, especially during the time period of 5-12 weeks, will be compared with FVIII activity measurements. Any abnormality of the liver parameters will lead to a retrospective immunogenicity assessment to determine

270-201 Amendment 8

anti-FVIII and capsid specific CTL. Anti-FVIII and capsid specific CTL assays will be performed on collected PBMCs.

Timing of assessment by these assays is provided in Table 9.1.2, Table 9.1.3, and Table 9.1.4.

9.7.5 Pharmacodynamics

The hFVIII antigen and activity level will be measured by an ELISA (antigen) and by one-stage clotting and/or chromogenic substrate assay (activity). Individual antigen and activity plasma plots will be prepared to assess changes over 16 weeks. FVIII activity measurements will be used to determine PD parameters.

If supported by FVIII activity data, non-compartmental analysis and observation will be used to estimate individual values of C_b (baseline concentration), C_{ss} (steady state concentration), T_{ss} (time to steady state), C(t) and AUC(0-t) where t is 16 weeks. Other parameters that may be used to describe individual FVIII protein and activity plasma profiles are C_{max} (maximum concentration) and C_{avg} (average concentration, AUC(0-t)/t). The PD parameters and dose will be used to assess clinical pharmacology.

Sample collection times are indicated in Table 9.1.2, Table 9.1.3, Table 9.1.4, and Table 9.1.5.

9.7.6 Exploratory Assessments

Blood samples will be collected at the time points indicated in Table 9.1.1, Table 9.1.2, Table 9.1.3, Table 9.1.4, and Table 9.1.5 to evaluate biochemical, molecular, cellular, and genetic/genomic aspects relevant to hemophilia A, coagulation, and/or AAV gene transfer, and to develop assays used for these evaluations. Subjects may choose to opt out of the exploratory genetic/genomic research being done to study or try to discover genes that are not yet known to be associated with hemophilia A.

Liver biopsy samples collected as part of the exploratory substudy may also be tested to evaluate biochemical, molecular, cellular, and genetic/genomic aspects relevant to hemophilia A, coagulation, and/or AAV gene transfer. Subjects participating in the substudy may choose to opt out of the exploratory genetic/genomic research being done to study or try to discover genes that are not yet known to be associated with hemophilia A.

All biomarker samples collected in this study may be used for exploratory biomarker research including evaluation of additional biomarkers not specifically listed in the protocol. In addition, samples collected for other purposes may be used for exploratory use once the primary use has been completed.

Proprietary and Confidential

270-201 Amendment 8

On an exploratory basis, samples may be fractionated prior to shedding analysis in order to better characterize the presence and location of vector DNA and/or vector capsid within each matrix. The fractionation may be performed with samples collected specifically for shedding analysis (saliva, blood, semen, urine, faeces), or by using exploratory samples, such as plasma, PBMCs, and red blood cells, collected under the study protocol.

9.7.7 Haemo-QoL-A Quality of Life Assessment

The Haemo-QoL-A is a patient-reported outcome (PRO) questionnaire which will be used to assess subject quality of life (QoL) during the study. Assessments will occur at the time points listed in the Schedules of Assessments.

Details regarding the QoL assessment will be included in the Study Reference Manual.

9.7.7.1 Liver Biopsy Substudy

The objectives of the liver biopsy substudy are considered exploratory.

Subjects who consent to the procedure will have a liver biopsy via either the transjugular or percutaneous (ultrasound-guided) route, according to the standard procedures of the institution. To enhance safety, all subjects will have an ultrasound exam of the liver within 28 days prior to the procedure (to ensure there is no obstruction to the liver that would interfere with the liver biopsy) and a FibroScan of the liver within one week before the liver biopsy (to correlate any histopathologic findings on the biopsy). Subjects will also undergo a pre-biopsy consultation with the investigator (treating hematologist).

Within 24 hours prior to the biopsy being performed, subjects must have a FVIII activity level of at least 50 IU/dL (or higher, depending on local guidelines and/or investigator discretion). FVIII activity levels for this purpose should be assessed at the local laboratory within 7 days before the biopsy, and again the day before the biopsy. As needed, subjects may be treated with additional exogenous FVIII replacement products in order to increase their FVIII activity levels to an appropriate level, under the supervision/instruction of the investigator, to ensure the safety of the subject during the procedure. This exogenous FVIII usage (if performed) should be recorded in the eCRF FVIII infusion pages under the category "Surgery/Procedure".

The liver biopsy should be performed in the morning, and the biopsy procedure and follow-up care should be done according to the local standard of care. Additional details for handling the biopsy specimens are provided in the Laboratory Manual.

270-201 Amendment 8

Following completion of the biopsy, the subject should remain in the hospital under observation for at least 4-6 hours. Overnight post-procedure observation may be done at the investigator's discretion and/or according to local guidelines.

Safety findings arising from the histopathological analysis of the biopsy sample are subject to Adverse Event reporting (Section 10), and such findings should be further assessed and followed-up as clinically appropriate and in order to safeguard the subject's ongoing medical care (this should be done in consultation with a hepatologist and/or other specialist clinicians if required). In the event fibrotic changes being observed on the biopsy sample, additional follow-up Fibroscans may be considered (with the frequency of subsequent scans at the discretion of the Investigator and/or hepatologist).

9.7.8 Safety Variables

Safety in this study will be determined from evaluation of AEs, clinical laboratory assessments with a particular attention to the liver function, vital signs assessments, physical examinations, and immunogenicity.

9.7.8.1 Adverse Events

The occurrence of AEs will be assessed continuously from the time the subject signs the ICF. The determination, evaluation and reporting of AEs will be performed as outlined in Section 10. Assessments of AEs will occur at the time points shown in Table 9.1.1, Table 9.1.2, Table 9.1.3, Table 9.1.4, and Table 9.1.5.

9.7.8.2 Clinical Laboratory Assessments

Specific visits for obtaining clinical laboratory assessment samples are provided in Table 9.1.1, Table 9.1.2, Table 9.1.3, Table 9.1.4, and Table 9.1.5. The scheduled clinical laboratory tests are listed in Table 9.7.8.2.1. Refer to the Study Reference Manual for instructions on obtaining and shipping samples.

Any abnormal test results determined to be clinically significant by the Investigator should be repeated (at the Investigator's discretion) until the cause of the abnormality is determined, the value returns to baseline or to within normal limits, or the Investigator determines that the abnormal value is no longer clinically significant.

All abnormal clinical laboratory results should be initialed and dated by an Investigator, along with a comment regarding whether or not the result is clinically significant. Each clinically significant laboratory result should be recorded as an adverse event.

The diagnosis, if known, associated with abnormalities in clinical laboratory tests that are considered clinically significant by the Investigator will be recorded on the AE CRF.

Blood Chemistry	Haematology	Urine Tests	Other
Albumin	Haemoglobin	Appearance	CRP
BUN	Haematocrit	Color	
Calcium	WBC count	рН	Coagulation Screen including:
Chloride	RBC count	Specific gravity	APTT
Total cholesterol	Platelet count	Ketones	PT/INR
CO_2	Differential cell count	Protein	TT
СРК	ABO blood typing*	Glucose	
Creatinine		Bilirubin	
Glucose		Nitrite	
Phosphorus		Urobilinogen	
Potassium		Haemoglobin	
Total protein			
Sodium			
Uric Acid			

Table 9.7.8.2.1: Clinical Laboratory Tests

BUN, blood urea nitrogen; CO₂, carbon dioxide; CRP, C-reactive protein; PT, prothrombin time; APTT, activated partial thromboplastin time; RBC, red blood cell; WBC, white blood cell; TT, thrombin time; INR, international normalized ratio. * ABO blood typing assessment should be completed at the next regularly scheduled study visit (or at least prior to the end of the subject's participation in the study).

9.7.8.3 Liver and Hepatitis Testing

Subjects will be screened for evidence of previous hepatitis B or hepatitis C infection at Screening. Subjects with documented results showing an absence of active hepatitis B or hepatitis C infection (as measured by positive surface antigen for hepatitis B or positive RNA testing for hepatitis C) 30 days prior to providing signed informed consent do not need to be screened again.

Evidence of ongoing hepatitis B or hepatitis C infection is exclusionary. Subjects with a history of hepatitis B or hepatitis C will be asked for information about the treatments received as part of their medical history assessment at Screening.

Subjects with a history of hepatitis B or hepatitis C infection prior to study entry will be tested for hepatitis B and hepatitis C reactivation at Week 16. Subjects who receive

therapeutic corticosteroids prior to Week 16 do not need to complete the Week 16 reactivation assessment; instead, they will be tested for hepatitis B and hepatitis C reactivation at the time points listed in Table 9.1.6.

A liver ultrasound and LTs at Screening will identify any significant hepatic dysfunction, which is defined as:

- More than 3x the normal ALT level
- More than 3x the normal bilirubin level
- More than 3x the normal Alkaline phosphatase level.
- INR ≥ 1.4 .
- Thrombocytopenia under 100 x 10⁹/L
- Liver ultrasound results indicative of a liver cirrhosis

Liver tests will be monitored on a regular basis, at the time points indicated in Table 9.1.1, Table 9.1.2, Table 9.1.3, Table 9.1.4, and Table 9.1.5. At each time point, the following LTs should be assessed:

Liver Tests (LTs)			
Alkaline Phosphatase	AST (SGOT)	Total Bilirubin	LDH
ALT (SGPT)	Direct Bilirubin	GGT	

ALT, alanine aminotransferase; AST, aspartate aminotransferase; GGT, gamma-glutamyltransferase; LDH, lactate dehydrogenase; SGOT, serum glutamic-oxaloacetic transaminase; SGPT, serum glutamic-pyruvic transaminase

Patients with ALT > 1.5 ULN during the study may undergo additional evaluations (eg, imaging studies including MRI or ultrasound, additional blood tests, and/or liver biopsy) at the discretion of the investigator.

9.7.8.4 HIV Testing

HIV testing will be performed at Screening. Subjects with documented negative results within the last 30 days prior to screening do not need to be retested.

9.7.8.5 Vital Signs, Physical Examinations and Other Observations Related to Safety

Vital signs will include seated systolic and diastolic blood pressure, heart rate, respiration rate, and temperature. Any clinically significant change in vital signs will be recorded as an AE.

270-201 Amendment 8

Systolic blood pressure, diastolic blood pressure, heart rate, respiration rate, and temperature will be assessed at Screening, Baseline, and at the beginning of each visit during the Post-Infusion Follow-Up and Safety Follow-Up periods. On the day of the BMN 270 Infusion, vital signs will be monitored prior to infusion, during the infusion every 15 minutes (\pm 5 minutes), following the infusion hourly (\pm 5 minutes) for 6 hours and then every 2 hours (\pm 15 minutes) for 6 hours and then at 4 hour intervals (\pm 15 minutes).

A complete physical examination is necessary during Screening/Baseline, at Week 16 and 52 and at the End of Years visits thereafter. A complete physical examination will include general appearance (head, eyes, ears, nose, and throat), cardiovascular, dermatologic, lymphatic, respiratory, gastrointestinal, genitourinary, musculoskeletal, and neurologic systems.

At other visits, brief physical examinations may be performed at the discretion of the investigator based on the subject's clinical condition. A brief physical examination will include general appearance, cardiovascular, respiratory, neurologic, dermatologic, musculoskeletal, and gastrointestinal assessments. Particular attention should be given to signs of bleeding, as well as assessing possible hemarthroses.

Height will be recorded at Screening only. Weight will be recorded at Screening, at Weeks 26 and 52 during Year 1, and then at the second Q12W visit each year and at every End of Years visit during Years 2-5.

9.7.8.6 Vector Shedding

Vector shedding has been extensively studied in all similar clinical trials performed to date. (Nathwani, 2014, N.Engl.J.Med.); (Manno, 2006, Nat.Med.); (Schenk-Braat, 2007, J.Gene Med.); (Croteau, 2004, Ann.Occup.Hyg.). In the literature referenced above, including Haemophilia B clinical studies utilizing AAV2 and AAV8, vector was no longer detectable after 40 days in blood, saliva, urine or stool, but in one study was detected in the seminal fluid but not in motile sperm (Manno, 2006, Nat.Med.). In these studies, the amount of vector present in these bodily fluids involved an extremely small fraction of the infused dose. More recent data from an ongoing AAV-FIX study demonstrates persistence of the vector in both the blood and the semen for at least 39 weeks (Miesbach, 2016, Haemophilia).

During the Post-Infusion Follow-Up period, subjects will undergo testing of various bodily samples to look for evidence of vector shedding for possible viral transmission. Bodily

fluids will be tested by PCR at the time points indicated in Table 9.1.2, Table 9.1.3, Table 9.1.4, and Table 9.1.5. Fluids tested will include:

- Blood
- Saliva
- Semen
- Urine
- Stool

Vector shedding will also be extensively studied in the present clinical trial, every other week between Weeks 4-16, then every 4 weeks to Week 52 until at least 3 consecutive negative results are obtained. Testing of semen will continue through Week 12, even if 3 consecutive negative results have been recorded in that compartment prior to that timepoint. Subjects who have not had 3 consecutive negative samples by Week 52 should continue to have PCR testing every 4 weeks until 3 consecutive negative samples are documented (or upon consultation between the Investigator and Medical Monitor). Subjects who meet the definition of treatment failure and wish to follow an abbreviated schedule (refer to Section 12.5.3 but who have not cleared vector shedding from all fluids must still provide samples for assessment until vector shedding has cleared: every 4 weeks (during Year 2), or every 6 weeks (during Years 3-5).

Contraception use may need to be extended beyond 26 weeks in individual subjects based on observed vector shedding in semen. After 6 months, subjects may stop contraception use only if they have had 3 consecutive negative semen samples (upon consultation between the Investigator and Medical Monitor).

Details for sample collection and storage are provided in the Laboratory Manual.

10 REPORTING ADVERSE EVENTS

10.1 Safety Parameters and Definitions

Safety assessments will consist of monitoring and recording protocol-defined AEs and SAEs; measurement of protocol-specified haematology, clinical chemistry, and urinalysis variables; measurement of protocol-specified vital signs; and other protocol-defined events of special interest that are deemed critical to the safety evaluation of the study drug.

10.1.1 Adverse Events

For this protocol, a reportable adverse event (AE) is any untoward medical occurrence (eg, sign, symptom, illness, disease or injury) in a subject administered the study-drug or other protocol-imposed intervention, regardless of attribution. This includes the following:

- AEs not previously observed in the subject that emerge during the course of the study.
- Pre-existing medical conditions judged by the Investigator to have worsened in severity or frequency or changed in character during the study.
- Complications that occur as a result of non-drug protocol-imposed interventions (eg, AEs related to screening procedures).

An adverse drug reaction is any AE for which there is a reasonable possibility that the study-drug caused the AE. "Reasonable possibility" means there is evidence to suggest a causal relationship between the study-drug and the AE.

Whenever possible, it is preferable to record a diagnosis as the AE term rather than a series of terms relating to a diagnosis.

10.1.1.1 Bleeding and Suspected Bleeding Events

All bleeding events and suspected bleeding events, regardless of the need for exogenous FVIII therapy as treatment, should be captured in subject diaries and recorded on the designated bleeding eCRF. Bleeding events and suspected bleeding events should not be reported as adverse events, with the following exception:

• All bleeding events and suspected bleeding events which meet one or more of the criteria for being serious (refer to Section 10.2) should be reported as serious adverse events (whether or not they are bleeding events that are normal sequelae of hemophilia, and whether or not they required exogenous FVIII as treatment).

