7.4.1 Liver Biopsy Substudy Risks and Benefits

Liver biopsy is considered a safe procedure, with serious complications occurring less than once in every 10,000 procedures (Grant, 2004). Although the theoretical risks of significant complications are extremely small, the main complications would include bleeding and bile leakage. Another theoretical complication is infection at the needle insertion site; the sterile technique used makes this risk extremely small.

The most common problems include mild pain and a minor decrease in blood pressure. More serious complications, such as bleeding, infection, and injury to nearby organs, are very rare, but the subject will be monitored appropriately to ensure correct management should any of these occur. Any complications related to the liver biopsy should be reported as adverse events, as outlined in Section 10. The liver biopsy is a standard investigation, and will be explained more fully by the experienced clinician performing the biopsy.

Each subject who participates in this optional substudy will have a comprehensive pre-/post-biopsy surveillance plan according to the standard procedures at the institution. Safety will be assessed by adverse event reporting and clinical laboratory assessments. Per the Investigator's discretion and/or according to local guidelines, the subject may be kept in overnight following the liver biopsy for additional safety monitoring; such an overnight stay would not be considered a hospitalization for serious adverse event (SAE) reporting purposes (refer to Section 10.4.1.7).

There is no direct benefit from participating in this study other than contributing to understanding the mechanism of action of BMN 270. Consenting into this specific substudy is optional and will not have any effect on the subject's continued participation in 270-201.

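### A non-serious bleed after the liver biopsy is a reportable adverse event under Sections 7.4.1 and 10.1.1 but barred from adverse event reporting by Section 10.1.1.1

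*Protocol*

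**What the plan says.** Section 7.4.1 of the protocol (Amendment 8) describes the risks of the optional liver biopsy substudy. It says that "the main complications would include bleeding and bile leakage", and it instructs sites: "Any complications related to the liver biopsy should be reported as adverse events, as outlined in Section 10".

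Section 10.1.1 defines a reportable AE. Its list of inclusions covers harm caused by study procedures as well as by the study drug: "Complications that occur as a result of non-drug protocol-imposed interventions (eg, AEs related to screening procedures").

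Section 10.1.1.1 gives a separate rule for bleeding. All bleeds and suspected bleeds, treated or not, "should be captured in subject diaries and recorded on the designated bleeding eCRF". It continues: "Bleeding events and suspected bleeding events should not be reported as adverse events, with the following exception". The exception reads: "All bleeding events and suspected bleeding events which meet one or more of the criteria for being serious (refer to Section 10.2) should be reported"; such bleeds go forward as SAEs. It is the only one.

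Section 9.7.8 sets out what the safety evaluation uses: "Safety in this study will be determined from evaluation of AEs, clinical laboratory assessments with a particular attention to the liver function", followed by vital signs, physical examinations and immunogenicity. Section 14.6 plans incidence summaries of AEs. Neither section names the bleeding eCRF.

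**The concern.** The substudy performs an invasive procedure in people with haemophilia, from which Section 7.4.1 says they gain no direct benefit. The protocol itself expects bleeding to be one of the main complications. For a puncture-site bleed or small haematoma that meets no seriousness criterion, an investigator who reads Section 7.4.1 reports an AE and one who reads Section 10.1.1.1 does not. Both have followed the protocol.

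At stake is consistent capture of procedural harm. Safety is a primary objective (Section 8), and the planned safety summaries draw on AEs. The same event could appear in those summaries from one site and be absent from another, and a reader of the AE tables could not tell the difference.

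**Working it through.** There is no planned figure to reproduce. The check sets the current provisions side by side for one event, a bleed caused by the biopsy.

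| Provision | Non-serious biopsy bleed | Serious biopsy bleed |
|---|---|---|
| 7.4.1, biopsy complications | AE | AE |
| 10.1.1, complications of protocol-imposed procedures | AE | AE |
| 10.1.1.1, bleeding events | Not an AE; diary and bleeding eCRF | SAE |

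The provisions agree in the right-hand column and contradict each other in the middle one.

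**Does another section resolve it?**

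1. Section 7.4.1 refers to Section 10 for how to report. Section 10 contains both 10.1.1 and 10.1.1.1, so the reference leads back to the conflict.
2. Section 9.7.7.1 sends safety findings from histopathology to AE reporting. It says nothing about bleeding from the procedure. Its surgery/procedure category is for FVIII infusions, not for bleeds.
3. Section 12.9 lists the biopsy procedures and gives no AE rule for bleeding.
4. Section 10.4.1.7 deals with hospital stays and does not classify non-serious bleeds.
5. Section 14.9 lets the SAP prevail over the protocol, but only for the text on statistical analysis. It cannot settle a reporting instruction to sites.

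None of these resolves it.

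**Does the seriousness exception make the gap unimportant?** Section 7.4.1 puts serious biopsy complications at less than 1 in 10,000 procedures. Section 14.7 allows up to 15 subjects. Assuming one biopsy each (the protocol does not state this) and all 15 consenting:

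P(at least one serious complication) ≤ 1 − (1 − 1/10,000)^15 ≈ 0.0015.

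On the protocol's own figure, then, the exception would seldom come into play. This is only an illustration. The rate refers to liver biopsy in general, its meaning of serious need not match the criteria in Section 10.2, and it says nothing about how often non-serious bleeds occur.

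**Where would the event go under 10.1.1.1?** To the diary and the bleeding eCRF. It stays in the database but is not coded as an AE, so it is outside the summaries in Section 14.6.

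**The case against.** The best reply is that little is lost. A biopsy bleed that meets a seriousness criterion, including one that prolongs hospitalization or counts as an important medical event, is reported as an SAE. Every other bleed is still recorded on the bleeding eCRF. The substudy is optional and exploratory, and because biopsies take place at least one year after infusion they cannot affect the Week 16 efficacy endpoint. All of this stands and limits the point to the classification of non-serious bleeds. It does not tell a site which instruction to follow.

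A reader might infer more than the documents support:

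- **That such events will usually be lost.** Section 10.1.1.1 is specific to bleeding, but 7.4.1 is equally specific to the biopsy. Which one a site would follow is conjecture.
- **That the overnight-stay wording blocks the seriousness exception.** Section 7.4.1 says "such an overnight stay would not be considered a hospitalization for serious adverse event (SAE) reporting purposes", but it refers to a discretionary stay for monitoring and points to Section 10.4.1.7, which limits its exemptions to cases where no AE has occurred. A bleed that itself requires or prolongs hospitalization remains serious under Section 10.2.
- **That the efficacy result is biased.** Section 9.7.3 counts bleeding episodes without mentioning procedural ones, while the objective in Section 8 concerns bleeds requiring treatment. Whether procedural bleeds count is a matter the SAP, not shown here, may properly decide.
- **That bleeding is the one principal risk.** It is named together with bile leakage, and milder problems are described as more common.

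**Conclusion.** The contradiction is real, lies in the current text, and is not resolved elsewhere in the protocol. It concerns one class of event: non-serious bleeding attributable to the liver biopsy or, through 10.1.1, to another protocol-imposed procedure. For that class, AE status depends on which section the site applies, and an event handled under 10.1.1.1 is absent from the AE summaries.

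The number of events cannot be estimated, because the documents give neither the number of subjects who will be biopsied nor a rate of non-serious bleeding. SAE reporting is intact. The conclusion rests on the wording of Sections 7.4.1, 10.1.1 and 10.1.1.1, and on 9.7.8 and 14.6 as the description of what the safety evaluation uses. It requires no assumption about how sites behave.

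**What to change.** Reconcile Sections 7.4.1, 10.1.1 and 10.1.1.1 by adding a second exception to 10.1.1.1: bleeding or suspected bleeding attributed to the liver biopsy, or to another protocol-imposed procedure, is reported as an AE whether or not it is serious. It continues to be entered in the diary and on the bleeding eCRF as now. Add a cross-reference to this exception in 7.4.1 and in 9.7.7.1. Whether these bleeds count in the bleeding outcome can be left to the SAP.

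The cost is one sentence and two cross-references in the next amendment, plus a note to sites. No visit, sample or procedure is added, and clinical management does not change.
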